9.3. Subject Consent

Informed consent is defined as legally effective, documented confirmation of a subject's (or their legally authorized representative's) voluntary agreement to participate in a particular clinical investigation after information has been given to the subject on all aspects of the clinical investigation that are relevant to the subject's decision to participate.

Pre-screening (visit to collect standard of care assessments according to institution) may be permitted prior to informed consent.

The Investigator(s) and/or staff delegated for this task are responsible for obtaining written informed consent and the HIPAA/data protection authorization from each potential subject before any study-

PR-NV16099

Version C

Page 75 of 144

Medtronic

specific procedures required by the clinical protocol are performed. Informed consent should be obtained in written format and using a form approved by the local IRB/REB and Medtronic. All subjects (or their legally authorized representative) must sign and date the Informed Consent Form and the HIPAA/data protection authorization prior to any procedures/tests that go beyond pre-screening assessments associated with the standard of care for subjects with intracranial aneurysms and before any study-related treatment assessments are administered and subject-related health information is entered into the study database. The Informed Consent Form and HIPAA/data protection authorization should be given to the subject (or their legally authorized representative) in a language he/she is able to read and understand.

Prior to inclusion in the study, it is the responsibility of the Investigator and/or staff delegated to this task to give each subject (or subject's legally authorized representative) full and adequate verbal and written information regarding the objective of this study and the confidentiality of the data collected. The process of obtaining informed consent must also be documented in the subject's file. The original or a copy of the signed Informed Consent Form should be filed in the hospital/clinical chart or with the subject's study documents. A copy of the consent and HIPAA/data protection authorization must be provided to the subject.

A thorough explanation will be provided to the subject (or subject's legally authorized representative) as to the nature and objectives of this study. Details of the study will be included according to country regulatory requirements which include but are not limited to the following:

- Purpose of the study
- Alternative treatments
- Procedures of the study including the need to return for 30-day, 180-day, 1-year, 2-year, and 3-year follow-up visits
- Participation is voluntary, and there is no penalty for withdrawal
- Potential risks and benefits of participation
- Compensation and expenses to subject
- Contact information to ask questions or voice concerns

Medtronic will maintain the sample Informed Consent Form and all materials used to consent including the HIPAA/data protection authorization within the Trial Master File.

PR-NV16099

9.4. Pre-Procedure Assessment

Subjects must undergo the device placement procedure within 30 calendar days of completion of all baseline assessment tests and procedures. On the day of the procedure and prior to treatment, the subject will again be evaluated and the following data shall be collected and recorded in the eCRF:

- Inclusion/exclusion criteria assessment
- Pregnancy test (Pregnancy test (serum or urine) only required for females of childbearing potential. Females who are surgically sterile or post-menopausal are not required to take a pregnancy test)
- Platelet count (can be done any time prior to the procedure)
- Platelet reactivity testing (If PRU is found below 60 or above 200 on the day of the procedure, the procedure should be delayed until it is within therapeutic range. In such cases, baseline measurements should be repeated if the next procedure is schedule >30 days from the initial planned procedure. If procedure is performed <30 days from the initial planned procedure. If procedure is performed <30 days from the initial planned procedure. If procedure is performed soldays from the initial planned procedure, the PRU measurements must be repeated but the other baseline measurements may be repeated per standard of care at the treating hospital). For OUS sites, a TEG test may be carried out instead of the PRU test (depending on PRU test availability). In cases where TEG test is carried out, the subject should have a pre-procedure therapeutic ADP% between >30% to <90%. If ADP% is <30% or >90% on the day of the procedure, the procedure should be delayed until it is within therapeutic range. In such cases, baseline measurements should be repeated if the next procedure is schedule >30 days from the initial baseline measurements. If procedure is performed <30 days from the initial baseline measurements must be repeated but the other baseline measurements may be repeated per standard of care at the treating hospital.
- Record protocol specified medications
- Record concomitant medications
- DSA imaging for final aneurysm measurements
- mRS assessment to be carried out by certified independent assessor at the site
- NIHSS
- Assessment of Adverse events of interest

PR-NV16099

Version C

9.5. Procedure

Eligible subjects will be treated with the Pipeline[™] Vantage Device per the IFU. During the procedure, Heparin should be administered as an anticoagulation agent.

Note: The Investigator(s) should review and understand the complete CIP and IFU prior to performing any study implant placement in this clinical study.

During or after the procedure, the following data shall be collected and recorded in the eCRF:

- Procedure date and time
- Primary interventionalist first and last name
- Target aneurysm location and dimensions
- Study device placement and resheathing information
- Device implant success (yes/no)- per device used
- Technical procedural success (per subject)
- Subject's radiation exposure (dose and fluoroscopy time)*
- Volume of contrast used
- Post-Pipeline[™] Vantage Device implant aneurysm occlusion, device placement and aneurysm status
- Procedural Complications
- Record protocol specified anticoagulation medications
- Record protocol specified DAPT
- ACT: Record at the start, after heparin is given, and at the end of the procedure if collected per standard of care
- Concomitant medications

*Take all necessary precautions to limit X-ray radiation doses to patients and themselves by using sufficient shielding, reducing fluoroscopy times, and modifying X-ray technical factors where possible.

Medications appropriate for general anesthesia will be administered using standard hospital practice. Capture all peri-procedural medications specific to the endovascular study procedure (e.g., anti-

		· · · · · · · · · · · · · · · · · · ·	111117 (11) (11) (11)
PR-NV16099	Version C	Page 78 of 144	Medtronic

hypertensives, prophylactic antibiotics) on the eCRFs. Anesthetics and other standard of care medications for surgical procedures (e.g., saline, povidone-iodine antiseptic, etc.) do not need to be collected.

Medications during treatment:

Anesthetics: The subject will undergo the Pipeline[™] Vantage placement under general anesthesia. Medications appropriate for general anesthesia will be administered using standard hospital practice. These are not required to be collected.

Anticoagulants: Heparin use will be required during Pipeline[™] Vantage placement with confirmation of anticoagulation via activated clotting time (ACT) prior to insertion of Pipeline[™] Vantage. During the procedure, ACT values should be monitored per standard practice and heparin dose adjusted, as clinically appropriate. Heparin may be used up to 24 hours after procedure. If medically indicated, heparin use may be continued after 24 hours, but the Investigator must document the reason for the continued use. Heparin use (dose in ug/dl), frequency, start and stop dates will be collected. ACT values at the start of procedure, during procedure and at the end of procedure will be collected per standard of care.

Other Procedural Medications: Any anti-thrombotic agents e.g., GPIIb3a inhibitors, Bivalirudin, Calcium Channel Blockers, Vasodilators, Antibiotics administered during the procedure shall be collected with their reason for use (prophylactic or for an AE intervention).

9.5.1. Ancillary Devices

Ancillary devices that may be required for the study procedure include, but are not limited to, access devices, intermediate support catheters, guidewires and microcatheters. Access devices, intermediate support catheters, and guidewires may be selected for use from FDA cleared devices as per Investigator preference and standard of care.

The Pipeline[™] Vantage implant is designed to be delivered through a compatible microcatheter of either 0.021 inch (0.53 mm) or 0.027 inch (0.69 mm) inside diameter and minimum 135 cm in length. Compatibility testing with the Phenom[™] 0.021" and 0.027" Microcatheter has been performed. Any compatible 0.021" and 0.027" microcatheter may be used but Phenom[™] Microcatheter is recommended. Refer to the below table (**Table 9-2**) for microcatheter compatibility for each device size.

Labeled Diameter (mm)	Compatible catheter inner diameter
2.50	
2.75	0.021 inch (0.53 mm)
3.00	

PR-NV16099	Version C	Page 79 of 144	Medtronic
3.25			
3.50		0.021 inch (0.53 mm) or 0.027 product label	inch (0.69 mm) per
4.00			
4.50			
5.00		0.027 inch (0.69	mm)
5.50			
6.00			

Ancillary Device Instructions: All endovascular devices are to be used in accordance with directions for use in the package insert approved by the FDA.

The use of guide catheters and microcatheters will be documented in the eCRFs.

9.5.2. Usage of Multiple Pipeline[™] Vantage Devices

Based on aneurysm and anatomical factors, if an investigator determines that multiple devices are required to cover the aneurysm neck adequately, an investigator may choose to deploy a maximum of 3 Pipeline[™] Vantage Devices that may be stacked at any point in the arterial vessel.

9.5.3. Adjunctive Device Use

Adjunctive devices are defined as devices (other than the Pipeline[™] Vantage Device) that are used to treat the target aneurysm.

Adjunctive device use (e.g. coils) is not allowed during the index procedure. Subjects that will require concomitant coiling should be excluded from the study (exclusion criteria). However, previous coiling failed subjects can be included.

9.5.4. Day 0 Imaging

At the beginning of the procedure prior to implantation, the following images shall be collected:

- 3-D DSA imaging pre-procedure to be used for final aneurysm measurements (if available)
- Two planes showing the entire vascular territory (either complete hemisphere or full posterior circulation filmed in the early venous phase)
- Views in the working projection with and without subtraction

At the end of the procedure after implantation, the following images shall be collected:

ADVANCE Clinical Investigation Plan Image: Clinical Investigation Plan PR-NV16099 Version C Page 80 of 144 Medtronic

- 3D DSA imaging (if available)
- Two planes showing the entire vascular territory (either complete hemisphere or full posterior circulation filmed in the early venous phase)
- Views in the working projection with and without subtraction

The Investigator or delegated study staff will submit procedural images to the core laboratory. The Investigator or delegated study staff will ensure that subject identifiers are removed from all submitted images. Image files/CDs should be labeled with the subject's study ID number.

9.5.5. Screen Failure

Subjects that are consented/enrolled in the study but do not undergo Pipeline[™] Vantage device implant attempt *i.e.,* puncture at the arterial access site (for not meeting eligibility criteria) should be exited from the study with the reason for exit recorded on eCRFs. Baseline CRFs should also be recorded for Screen Failure subjects.

9.5.6. No Treatment of an Eligible Subject with the Pipeline[™] Vantage Device

In the event that the subject was confirmed to be eligible for the study at baseline, signed informed consent, but the target intracranial aneurysm is not treated with the Pipeline[™] Vantage Device at the initially scheduled procedure, the subject may be brought in later to undergo the Pipeline[™] Vantage Device. In this case:

- In the event the subject does not meet protocol specified PRU value range (≥60 and ≤200) or TEG value range (>30% to <90%) on the day of the procedure, the procedure should be delayed (and no puncture at the arterial access site performed) until a protocol specified therapeutic range for PRU/TEG is achieved. The day of the puncture at the arterial access site is considered day 0.
- 2) In cases where PRU/TEG criteria is met and puncture at the arterial access site is performed, and the aneurysm is not able to be accessed or a study device unable to be deployed, the reasons of the inaccessibility of the aneurysm or study device failing to deploy (incomplete treatment) will be captured. Any alternate treatments if received will be captured. Such subjects will not be included in the per-protocol analysis. In cases where the subject is brought back at a later time and undergoes a second procedure with the study device, the date of the first intervention will be considered Day 0. The second intervention (if successful) will not be considered a retreatment. The subject must be brought back for the second intervention within 6 weeks of the initial attempted treatment.

PR-NV16099

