Aneurysm Dome		Maximum horizontal diameter of the aneurysm.	
Aneurysm Neck		Opening of the aneurysm where it meets the parent vessel	
Aneurysm Occlusion		 According to the Raymond–Roy Scale¹: Class 1: Complete Occlusion – complete obliteration of the aneurysm. Class 2: Residual Neck – persistence of any portion of the original defect of the arterial wall as seen on any single projection, but without opacification of the aneurysmal sac. Class 3: Residual Aneurysm– any opacification of the aneurysmal sac. 	
Attempted Procedure		Any procedure where Pipeline [™] Vantage Embolization Device with Shield Technology [™] was attempted i.e., successful puncture at the arterial access site.	
Bleeding Complications per GUSTO		 Bleeding complications shall be adjudicated using the GUSTO bleeding criteria which includes categorizing all bleeding events into the following categories: Severe or Life-threatening: Intracerebral hemorrhage Resulting in substantial hemodynamic compromise requiring treatment Moderate: Requiring blood transfusion but not resulting in hemodynamic compromise Mild Bleeding that does not meet above criteria 	
Cerebral Infarction		Evidence of new ischemic changes (infarction) on imaging. Further characterized as:	

PR-NV16099	Version C	Page 13 of 144 Mectronic
		 Asymptomatic: no associated focal neurological deficit symptoms (i.e., Silent Infarctions) Symptomatic: focal neurological deficit
Contrast Induced Complications		symptoms lasting less than 24 hours Complications arising due to the use of contrast agent used for imaging requirements during study procedure(s).
Delayed Intra-Cranial Hemorrhage (IC	н)	Any intracranial hemorrhage occurring >30 days post- procedure
Device Deficiency (DD)		Inadequacy of a medical device with respect to its identity, quality, durability, reliability, safety or performance. (ISO 14155:2011 3.15) Note: Device deficiencies include malfunctions, use errors, and inadequate labeling.
Device Movement		Unintended Pipeline stent (braid) Movement (as observed/discerned on imaging) of the implanted device following deployment.
		Device movement will be further characterized by:
		 Timing: Intra-procedural: Observed during the study index procedure
		 Post-procedural: Observed at a follow-up time point
		 Foreshortening: Movement on either or both ends of the device in opposite direction towards the aneurysm neck.
		 Migration: Movement of device where both ends move in a single direction away from the aneurysm neck.

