5.1.2.1. Secondary Endpoint(s)

The following will be assessed for the effectiveness outcome measures:

- 1. Incidence of successful device implantation at the target site
- 2. Incidence of complete aneurysm occlusion (Raymond Roy Class 1) at 1- and 3-years postprocedure
- 3. Incidence of target aneurysm recurrence at 1- and 3-years post-procedure

For the purposes of this study protocol, successful device implantation will be presented in terms of Procedural Technical Success and Device Technical Success. Procedure technical success is measured by the rate of successful implantation of the study device during the study index procedure at the target site regardless of the number of devices deployed and implanted at the target site. Device technical success is measured by the rate of successful study device implantation at the target site with the total number of devices attempted to be deployed.

Successful device implantation and retreatment will be site reported. Aneurysm occlusion class, recurrence, and parent artery stenosis will be assessed by the independent Imaging Core Lab.

The following will be assessed for the secondary safety endpoints:

- 1. Incidence of major stroke in the territory supplied by the treated artery or neurological death at 2- and 3-years post-procedure
- 2. Incidence of major stroke in the territory supplied by the treated artery or neurological death at 30 days post-procedure
- Incidence of delayed intraparenchymal hemorrhage >30 days post-procedure through 1-year post-procedure
- Incidence of subjects with disabling strokes that have a mRS decline to a score of 3 or more (mRS ≥ 3) due to a stroke-related cause assessed at a minimum of 90 days post-stroke event at 1 year, 2 year, and 3 year post-procedure

The events comprising the safety endpoints will be adjudicated by the independent CEC.

PR-NV16099

Version C

Page 47 of 144

6. Study Design

The study is a prospective, global, multi-center, single-arm IDE clinical study evaluating the performance of the Pipeline[™] Vantage Device. The Pipeline[™] Vantage Device is investigational in the United States and Canada.

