9.8. Retreatment

At the Investigator's discretion, the target aneurysm may be retreated at any time during the study. The retreatment procedure can include any endovascular or surgical intervention including the implant of the Pipeline[™] Vantage Device. In such situations, the date that the subject receives the initial Pipeline[™] Vantage Device implant (and not the date of the retreatment) will be considered Day 0.

Reason(s) for retreatment of aneurysm shall be documented:

- Device Movement
 - Foreshortening (Peri-procedural or Delayed)
 - Migration
- Aneurysm Growth
- Aneurysm Rupture
- Aneurysm Non-Occlusion
- Insufficient Neck Coverage

Type of Retreatment will be documented:

- Planned
- Unplanned

A retreatment will be considered an "Unscheduled Visit" and subjects will be required to undergo the following study assessments:

- Full neurological exam and assessment of aneurysm symptoms (new, worsened, improved, stable)
- Record concomitant and protocol-specified medications
- Imaging (per standard of care)
- NIHSS
- mRS assessment to be carried out by a certified independent assessor at site
- Assessment of Adverse events

		· · · · · · · · · · · · · · · · · · ·	and the second sec
PR-NV16099	Version C	Page 83 of 144	Medtronic

Data will be collected for all retreatment procedures in the Retreatment eCRFs. Retreatments should be reported as an SAE.

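### After a failed first attempt Day 0 stays at the first puncture, although implantation may follow up to 42 days later, so the two secondary safety endpoints cut at 30 days can misplace peri-implant events

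*Combined protocol and SAP*

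**What the plan says.** Section 9.5.6 covers a subject whose artery was punctured but whose aneurysm could not be reached or whose device could not be deployed. If that subject returns for another procedure, "the date of the first intervention will be considered Day 0". The interval is bounded: "The subject must be brought back for the second intervention within 6 weeks of the initial attempted treatment". The repeat procedure has its own status: "The second intervention (if successful) will not be considered a retreatment".

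Section 5.1.2.1, repeated in 13.8.3, lists two secondary safety endpoints that use a 30-day cut. The first looks at early events: "Incidence of major stroke in the territory supplied by the treated artery or neurological death at 30 days post-procedure". The second looks only at bleeding beyond the cut: "Incidence of delayed intraparenchymal hemorrhage >30 days post-procedure through 1-year post-procedure".

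The Glossary places the index procedure at the first intended procedure with a successful puncture, and links the study procedure to Day 0. I found no text that times either endpoint from the implant date for second-attempt subjects.

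Three other sections use a Day 0 anchor. Section 9.8, on retreatment, takes the date of the initial implant: "and not the date of the retreatment) will be considered Day 0". Section 11.1.3 identifies the investigational device as the one used in the Day 0 procedure. Section 11.1.8 assesses procedural causality against the Day 0 procedure, describes it as the first application of the device, and leaves out later procedures.

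**The concern.** The two endpoints separate events around device placement from later ones. That works when puncture and implantation fall on the same day. Under 9.5.6 they can be 42 days apart, which is longer than the 30-day cut. The early window can then close before the device is in place, and a complication of placing it is reported as late or is absent from the early count.

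Both endpoints are expected to be sparse, so one misplaced event could be the only one in its category. The subjects concerned are those whose first procedure failed. They are in the ITT population, which section 13.3 makes primary for all analyses.

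**Working it through.** **Inputs.** Longest gap to the second attempt: 6 weeks (9.5.6). Endpoint cut: 30 days (5.1.2.1). 30-day visit: ±7 days (9.9.1). 1-year visit: ±56 days (9.9.3). The plan states no figure for this situation, so there is none to reproduce.

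**Step 1: gap against cut.** 6 × 7 = 42 days, and 42 − 30 = 12. An implantation on any of the 12 days from day 31 to day 42 falls after the 30-day window has closed.

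**Step 2: post-implant days left in the window.** For implantation on day d after the first puncture, this is max(0, 30 − d). An implant-day bleed counts as delayed when d > 30.

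| Implant day d | Post-implant days inside the 30-day window | Implant-day bleed scored as delayed? |
|---|---|---|
| 7 | 23 | no |
| 14 | 16 | no |
| 21 | 9 | no |
| 28 | 2 | no |
| 30 | 0 | no |
| 31–42 | 0 | yes |

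Complete misplacement therefore needs d between 31 and 42. A smaller d only shortens the window. With d = 14, for example, a qualifying event more than 16 days after implantation is already beyond the cut.

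**Step 3: the 30-day visit.** It falls on days 30 ± 7, that is 23 to 37. For implantation on day 42 it takes place before the device is implanted.

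**Step 4: the 1-year endpoints.** The 1-year visit falls on days 365 ± 56, that is 309 to 421. With d = 42, post-implant time is 365 − 42 = 323 days at the nominal date and 309 − 42 = 267 days at the earliest visit. A stroke in the 30 days after a day-42 implantation falls by day 42 + 30 = 72, well inside the primary safety year.

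**Step 5: how many subjects.** The documents report no rate for subjects who fail, return and are then implanted. The nearest figure is SHIELD OUS (4.2.7), with 200/204 deployed, so 4/204 = 2.0% were not. Table 4-1 puts the implanted set at 200 of 204, so those 4 appear never to have been implanted. PFLEX (4.2.8) had 50/50 deployed. I therefore use 0 to about 2 per 100 as an assumption.

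**Step 6: weight of one event.** With 100 subjects one event is 1/100 = 1 percentage point. For 30-day major stroke or neurological death, the plan reports none in PREMIER and PFLEX and 6/204 = 2.9% in SHIELD OUS, or about 0 to 3 events per 100. For delayed intracerebral hemorrhage it reports 0.73%, 0 and 0% in PREMIER, SHIELD OUS and PFLEX, or about 0 to 1 per 100.

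**The case against.** The first-puncture anchor is deliberate and defensible. Index procedure, ITT entry and Day 0 all depend on a successful puncture, which gives one time origin and captures harm from the failed attempt. Moving every clock to the implant date would start follow-up at a post-baseline event. This stands, and it is why the fix leaves Day 0 and the yearly windows alone.

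The two endpoints are descriptive: section 13.8.3 tests no secondary endpoint against a threshold. That also stands, and it limits the consequence to reported counts.

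The per-protocol analysis excludes subjects whose implantation failed at the index procedure, so each endpoint is also shown without them. That removes the subjects but does not correct the ITT counts.

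Section 13.1 defers detail to a later SAP, and one could read the time after the procedure as time after actual placement. But 9.5.6 already states Day 0 for exactly this case, so silence elsewhere does not displace it.

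A reader might infer three stronger points that the documents do not support:

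- **That both primary endpoints are compromised.** A peri-implant stroke still counts within the year. A nominal 323 days of exposure lies inside the 309 to 421 days accepted for everyone. The 267-day figure needs the latest second attempt and the earliest visit together.
- **That about 2 in 100 subjects are affected.** The SHIELD OUS figure describes subjects without deployment, not subjects implanted later.
- **That 9.8 contradicts 9.5.6 outright.** Section 9.8 governs retreatment, and 9.5.6 says the second attempt is not one. The two rules meet only for a subject implanted at a second attempt and later retreated.

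**Conclusion.** The point holds for two secondary safety endpoints. Followed as written, the plan omits from the 30-day endpoint a major stroke or neurological death at an implantation on days 31 to 42, and labels an intraparenchymal hemorrhage there as delayed. Earlier second attempts lose d of the 30 post-implant days.

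The number of subjects is small: 0 to about 2 per 100 by assumption, and fewer if not all return or most return before day 31. Each misplaced event shifts a rate by 1 percentage point per 100 subjects. No primary endpoint decision, sample size or power figure changes. It merits correction because the affected counts are near zero and the rule places events on the wrong side of a peri-procedural boundary.

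A related gap is attribution. Read literally, 11.1.3 and 11.1.8 tie device and procedure to Day 0, so a complication of a second-attempt implantation may not be attributed to either. Yet 11.1.8 also describes the Day 0 procedure as the device's first application, which for these subjects may be the second attempt.

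**What to change.** Keep Day 0, ITT entry and the 1-, 2- and 3-year windows at the first puncture. For the 30-day and delayed-hemorrhage endpoints only, add this derivation to 9.5.6 and the SAP:

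- An event is 30-day (peri-procedural) if it occurs between the first and second attempt, or within 30 days after any study-device attempt. Attempts here are those under 9.5.6; a retreatment under 9.8 does not restart the window.
- A hemorrhage is delayed only if it occurs more than 30 days after the latest attempt.
- Results timed from the first puncture are reported as a sensitivity analysis.

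State also that the Day 0 wording in 9.8, and the Day 0 procedure in 11.1.3 and 11.1.8, must be reconciled with 9.5.6 for second-attempt subjects.

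The cost is a few sentences of protocol text and a derivation rule that uses procedure dates already recorded under 9.5. The drawback is an early window that is not quite uniform: up to 42 + 30 = 72 days from the first puncture for a few subjects.
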